2.2 ENDPOINTS

2.2.1 Primary Endpoint

- Proportion of participants achieving urate level $\leq 0.30\text{mmol/L}$ at 24 weeks.

2.2.2 Secondary Endpoints (assessed at week 24 and 52, and for extension study also at week 104 and 156)

- Proportion of participants achieving urate level $\leq 0.3\text{mmol/l}$ and $\leq 0.36\text{mmol/l}$
- Prospectively gathered number of days of self-reported gout flare over course of study
- Size in mm of the largest tophus at baseline (index tophus)
- The number of clinically evident tophi
- Prospectively gathered self-reported quality of life during/following gout flare evaluated using the EQ-5D-5L questionnaire over course of study
- Prospectively gathered data on days lost at work due to gout flare over course of study
- Prospectively gathered number of scheduled and unscheduled medical appointments/ hospital admissions due to gout over course of study
- Self report of number of doses of medication omitted in preceding 2 weeks will be collected at all study visits
- Plasma oxypurinol levels will be measured at study visits where possible
- Proportion of patients achieving a dose reduction of urate lowering therapy in the extension phase whilst maintaining target urate levels.
- Proportion of patients achieving sustained dietary modifications with reduction of urate levels, and/or further reduction of urate lowering therapy dose in the extension phase.

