6.1.4 Follow-up visit week 52 (and for extension study week 104 and 156)

Participants will be invited to the RDU clinic for review of secondary outcomes, or alternatively if hospital attendance is not appropriate due to recommendations to self-isolate or maintain social distancing due to the coronavirus pandemic then this assessment will be made by telephone. The patient diaries generated by the GoutSMART application will be reviewed and any adverse advents recorded. All participants will be asked to record the number of doses of medication missed in the preceding 2 weeks. A physical examination will be performed to assess the size and number of tophi or submitted images will be reviewed. Finger prick and/or serum urate will be measured along with blood tests of renal and liver function tests and oxypurinol levels.

All participants completing the study at week 52 will be offered participation of the extension phase of the study. Written information will have been provided prior to their week 52 review about the extension. Consent will be gained from those choosing to participate in the extension phase. A treatment plan will be formulated for all participants. Participants of the intervention arm in remission will be offered to reduce the dose of their urate lowering medication and self-reassess every two weeks (update urate levels, entering disease activity

data) until remission maintenance is achieved. Feedback will be provided in the usual GoutSMART application manner. Participants of the control arm will continue as per routine care. Once remission maintenance is achieved monthly urate reading will be requested. The participant will be asked to enter additional urate readings and QoL information during flares.

For those opting into the dietary lifestyle intervention arm, a personal management plan with dietary adjustments where appropriate will be formulated based on the Food Frequency Questionnaire which each participant will fill in at baseline. Participants will be asked to perform weekly urate measurements, weight measurements and report on flares via the app. Feedback will be provided by the research team at least weekly for the first 4 weeks, then monthly for three months. Participants will be asked to fill in the Food Frequency Questionnaire at extension baseline, monthly for three months and at the end of study.

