8.2 PROPOSED ANALYSES

The primary outcomes of the study will be the proportion of participants achieving urate level $\leq 0.3\text{mmol/l}$ at 24 weeks in participants receiving supported self-management compared to those receiving usual care. Comparison of proportions will be performed using the Chi-square test of independence, or Fishers Exact test for where expected values in any cell of the contingency table are less than 5, with results displayed as frequency (percentages). The proportion of participants achieving serum urate level $\leq 0.3\text{mmol/l}$ at all subsequent assessments will be analysed in the same fashion. Patients with undetectable levels of oxypurinol will be deemed to be non-compliant and a similar analysis will compare the proportion of participants in each treatment allocation that are non-compliant. For these analyses an intention to treat analysis will be performed with participants that have dropped out of the study being included as failing to reach target, or non-compliant with medication respectively.

Continuous outcome measures include the size in mm of the largest tophus at baseline (index tophus) measured at 52 weeks, and the number of clinically evident tophi evaluated at 52 weeks. Further continuous outcomes include the number of days lost at work due to gout flare, number of scheduled and unscheduled medical appointments/ hospital admissions, self report of number of doses of medication omitted in 2 weeks prior to study visits at week 24 and 52. Two-tailed independent student t-tests will be applied for between group comparisons of normally distributed data. Results will be displayed as mean \pm standard deviation (SD). A Mann Whitney U test (MWU) will be applied when the variables are not normally distributed, with results given as median (interquartile range IQR). Although a nominal value of significance of $p<0.05$ for these exploratory measures will be adopted, given the number of secondary outcomes listed a Bonferroni correction will be applied and reported alongside each result.

Although health reported quality of life data will be gathered this is exploratory data that will not be analysed directly but be used to inform the design of a larger health economic study.

Statistical analysis will be performed using Minitab version 16 (Minitab Inc., Pennsylvania, US) or the Statistical Package for Social Services version 19 (SPSS IBM Corp, NY State, US).

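### Section 8.2 corrects the secondary outcomes by single-step Bonferroni with no stated divisor; Holm over a named family gives the same error control and never less power

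*Combined protocol and SAP*

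**What the plan says.** Section 8.2 first sets the working criterion for the secondary measures: "Although a nominal value of significance of $p<0.05$ for these exploratory measures will be adopted". It then adds that "given the number of secondary outcomes listed a Bonferroni correction will be applied and reported alongside each result". It prints no divisor, no corrected threshold and no list of the tests to be corrected. The continuous outcomes are compared as follows: "Two-tailed independent student t-tests will be applied for between group comparisons of normally distributed data", with Mann-Whitney for non-normal data. The binary outcomes are compared by chi-square or Fisher's exact test.

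Section 2.2.2 lists 11 secondary bullets, headed as "assessed at week 24 and 52, and for extension study also at week 104 and 156". They do not match the comparisons in section 8.2 one for one:

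- Quality of life (EQ-5D-5L) is listed, but section 8.2 says "this is exploratory data that will not be analysed directly".
- Flare days are listed ("Prospectively gathered number of days of self-reported gout flare over course of study") but have no named test. Neither does the 0.36 mmol/l threshold.
- Dose reduction has no named test, and section 6.1.4 describes it for one arm: "Participants of the intervention arm in remission will be offered to reduce the dose of their urate lowering medication". The dietary substudy in section 3.2 is likewise offered to the active arm only.

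**The concern.** Two things are open to improvement. The first is the method. Single-step Bonferroni compares every p-value with 0.05/m, where m is the number of tests. Holm compares only the smallest p-value with 0.05/m and relaxes the threshold after each rejection, yet keeps the same family-wise bound under any dependence between outcomes. Bonferroni's usual advantage is that it gives matching simultaneous confidence intervals, and this plan does not use them.

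The second is that m is undefined. An analyst could count the outcomes in that paragraph of 8.2, all tests in 8.2, or the bullets of 2.2.2, with or without the extension visits. The corrected result beside each outcome would differ according to that choice, which could be made after the data are seen. In a trial of this size, some real differences would be reported as not surviving correction when an equally strict procedure would have kept them.

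**Working it through.** The plan gives no multiplicity figure to reproduce, so the check starts by counting.

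**1. Between-arm secondary tests specified through week 52**

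| Outcome | Visits | Tests |
|---|---|---|
| Urate ≤0.3 mmol/l | 52 | 1 |
| Oxypurinol non-compliance (visits from section 3.1) | 24, 52 | 2 |
| Index tophus size | 52 | 1 |
| Number of tophi | 52 | 1 |
| Work days lost | – | 1 |
| Appointments/admissions | – | 1 |
| Missed doses | 24, 52 | 2 |
| **Total** | | **9** |

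Splitting appointments/admissions into three gives 9 + 2 = 11. Adding weeks 104 and 156 for urate and oxypurinol gives 9 + 4 = 13, or 15 with the split. The last six tests in the table (tophus size to missed doses) are those in the paragraph that carries the correction.

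**2. What a divisor of 11 would do**

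The threshold would be 0.05/11 = 0.00455. The family-wise bound is the number of tests times that threshold:

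- 9 tests: 9 × 0.00455 = 0.041, stricter than needed
- 11 tests: 0.050, exact
- 13 tests: 0.059, too lenient
- 15 tests: 0.068, too lenient

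The direction of any error therefore depends on which visits are in the family.

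**3. Holm against Bonferroni with m = 9**

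Bonferroni uses 0.05/9 = 0.00556 for every test. Holm orders the p-values and uses 0.05/9 = 0.00556, 0.05/8 = 0.00625, 0.05/7 = 0.00714 and so on up to 0.05, stopping at the first failure. No Holm threshold is below the Bonferroni one, so Holm rejects at least the same set.

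**4. Power per true effect**

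Inputs: 34 and 17 participants (section 8.1), two-sided t-test, and an assumed normal effect of d = 1.0 SD. The noncentrality is d/√(1/34 + 1/17) = 1.0/0.297 = 3.37 on 34 + 17 − 2 = 49 degrees of freedom.

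| Single-step threshold | Critical t | Power |
|---|---|---|
| 0.05 (nominal) | 2.01 | 91% |
| 0.05/6 | 2.75 | 73% |
| 0.05/9 | 2.90 | 68% |
| 0.05/11 | 2.97 | 65% |
| 0.05/13 | 3.03 | 63% |

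Holm was simulated over nine outcomes with correlation 0.3 (40,000 replicates):

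| True effects among nine | Bonferroni/9 | Holm/9 |
|---|---|---|
| Two | 68% | 69% |
| Four | 68% | 71% |
| All nine | 68% | 81% |

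With no true effect, the simulated family-wise error is 4.5% for both. With two true effects it is 3.7% for Bonferroni and 4.4% for Holm, so Holm uses more of the permitted 5% without exceeding it.

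At 0.8 SD, power is 40% at 0.05/11 and about 43% at 0.05/9. Holm over nine gives 43% (two true effects), 45% (four) and 53% (all nine).

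**The case against.** The strongest reply is that little depends on this. Nominal p<0.05 is the adopted criterion, the corrected result is only reported beside it, and section 8.1 calls this a feasibility study meant to inform a larger one. That stands, and it limits the point to how the corrected results are read.

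A second reply is that Holm's own gain is small when few effects are real: about 1 point with two true effects and 3 with four, at 1.0 SD. That also stands. The larger figure needs all nine outcomes to differ.

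A third reply is that the normal model is a rough guide. Three of the nine tests are binary, and the others are sizes, counts or days that may be skewed. This affects the power figures, but not the ordering of the two methods, which holds for any valid p-values.

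A reader might go further and infer that the plan over-corrects because it charges for listed outcomes that are never tested. The documents do not support that. The phrase about the number of outcomes may explain why a correction is made without setting m, and it may refer only to the outcomes named in the same paragraph. Quality of life is the only outcome expressly left unanalysed; the continuous outcomes are introduced as an open list, so flare days could still be tested. If the extension visits are counted, 11 is too small, not too large. A reader might also count only the six tests in the continuous paragraph, but that omits urate at week 52 and oxypurinol at two visits, which the preceding paragraph specifies.

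**Conclusion.** The point holds as a minor improvement. For whatever set of tests the sponsor intends, Holm gives the same family-wise guarantee as the planned Bonferroni correction and is never less powerful. The family and divisor should be stated in either case.

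Over nine tests at 1.0 SD, the gain from Holm is 1 to 3 points per true effect when two to four effects are real, and 13 points when all nine are. If the analyst would otherwise have divided by 11, moving to Bonferroni over nine adds a further 3 points (65% to 68%). That second gain is conditional on a reading that the text does not settle.

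The figures assume 34 and 17 analysed participants, normal outcomes and correlation 0.3. Section 8.1 says that its numbers allow for 15% drop-out; fewer analysed participants would lower power under both methods. No conclusion about the primary outcome is affected.

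**What to change.** Replace the Bonferroni sentence in section 8.2 with:

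> Holm-adjusted p-values will be reported alongside each nominal p-value. The family is the between-arm secondary tests performed through week 52: urate ≤0.3 mmol/l at week 52, oxypurinol non-compliance at weeks 24 and 52, index tophus size and tophus number at week 52, work days lost, appointments/admissions, and missed doses at weeks 24 and 52 (nine tests, increased if further between-arm tests such as flare days are performed). Outcomes not tested between arms are not counted. Extension-visit tests form a separate, stated family.

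Any additions to the nine, such as splitting appointments/admissions, should be settled before the data are examined. A separate extension family carries its own 5% error rate, so the plan should say that this is intended. There is a reason for it: the extension adds participants randomised 1:1 and has its own power calculation.

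The cost is one paragraph. Holm-adjusted p-values come by hand from the ordered p-values already produced. No new data, tests or software are needed.

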9 ADVERSE EVENTS

Adverse side effects from allopurinol and febuxostat are rare, with the commonest side effect being of skin rash. All participants will be informed of potential side effects of their treatment in line with usual clinical practice and be able to contact the study team directly to discuss any concerns. The participants' usual primary care physician will be notified simultaneously with details of any medication change to ensure that the primary care records remain accurate and to minimize the risk of drug interactions.

10 OVERSIGHT ARRANGEMENTS

10.1 INSPECTION OF RECORDS

Investigators and institutions involved in the study will permit trial related monitoring and audits on behalf of the sponsor, REC review, and regulatory inspection(s). In the event of audit or monitoring, the Investigator agrees to allow the representatives of the sponsor/direct access to all study records and source documentation. In the event of regulatory inspection, the Investigator agrees to allow inspectors direct access to all study records and source documentation.

11 GOOD CLINICAL PRACTICE

11.1 ETHICAL CONDUCT

The study will be conducted in accordance with the principles of the International Conference on Harmonisation Tripartite Guideline for Good Clinical Practice (ICH GCP).

11.2 INVESTIGATOR RESPONSIBILITIES

The Investigator is responsible for the overall conduct of the study at the site and compliance with the protocol and any protocol amendments. Responsibilities may be delegated to an appropriate member of study site staff.

11.2.1 Informed Consent

The Investigator is responsible for ensuring informed consent is obtained before any protocol specific procedures are carried out. The decision of a participant to participate in clinical research is voluntary and should be based on a clear understanding of what is involved.

Participants must receive adequate oral and written information – appropriate Participant Information and Informed Consent Forms will be provided. The oral explanation to the participant will be performed by the Investigator or qualified delegated person, and must cover all the elements specified in the Participant Information Sheet and Consent Form.

The participant must be given every opportunity to clarify any points they do not understand and, if necessary, ask for more information. The participant must be given sufficient time to consider the information provided. It should be emphasized that the participant may withdraw their consent to participate at any time without loss of benefits to which they otherwise would be entitled.

The participant will be informed and agree to their medical records being inspected by regulatory authorities and representatives of the sponsor(s).

The Investigator or delegated member of the trial team and the participant will sign and date the Informed Consent Form(s) to confirm that consent has been obtained. The participant will receive a copy of this document and a copy filed in the Investigator Site File (ISF) and participant's medical notes (if applicable).

11.2.2 Study Site Staff

The Investigator must be familiar with the protocol and the study requirements. It is the Investigator's responsibility to ensure that all staff assisting with the study are adequately informed about the protocol and their trial related duties.

11.2.3 Data Recording

The Principal Investigator is responsible for the quality of the data recorded in the CRF at each Investigator Site.

11.2.4 Investigator Documentation

The Principal Investigator will ensure that the required documentation is available in local Investigator Site Files (ISFs).

11.2.5 GCP Training

All researchers will be expected to have undertaken GCP training in order to understand the principles of GCP. GCP training status for all investigators will be indicated in their CVs.

11.2.6 Confidentiality

All laboratory specimens, evaluation forms, reports, and other records must be identified in a manner designed to maintain participant confidentiality. All records must be kept in a secure storage area with limited access. Clinical information will not be released without the written permission of the participant. The Investigator and study site staff involved with this study may not disclose or use for any purpose other than performance of the study, any data, record, or other unpublished, confidential information disclosed to those individuals for the purpose of the study. Prior written agreement from the sponsor or its designee must be obtained for the disclosure of any said confidential information to other parties.

11.2.7 Data Protection

All Investigators and study site staff involved with this study must comply with the requirements of the Data Protection Act 1998 with regard to the collection, storage, processing and disclosure of personal information and will uphold the Act's core principles. Access to collated participant data will be restricted to individuals from the research team treating the participants, representatives of the sponsor(s) and representatives of regulatory authorities.

Computers used to collate the data will have limited access measures via user names and passwords.

Published results will not contain any personal data that could allow identification of individual participants.

12 STUDY CONDUCT RESPONSIBILITIES

12.1 PROTOCOL AMENDMENTS

Any changes in research activity, except those necessary to remove an apparent, immediate hazard to the participant in the case of an urgent safety measure, must be reviewed and approved by the Chief Investigator.

Amendments will be submitted to a sponsor representative for review and authorisation before being submitted in writing to the appropriate REC, and local R&D for approval prior to participants being enrolled into an amended protocol.

12.2 MANAGEMENT OF PROTOCOL NON COMPLIANCE

Prospective protocol deviations, i.e. protocol waivers, will not be approved by the sponsors and therefore will not be implemented, except where necessary to eliminate an immediate hazard to study participants. If this necessitates a subsequent protocol amendment, this should be submitted to the REC, and local R&D for review and approval if appropriate.

Protocol deviations will be recorded in a protocol deviation log and logs will be submitted to the sponsors every 3 months. Each protocol violation will be reported to the sponsor within 3 days of becoming aware of the violation. All protocol deviation logs and violation forms should be emailed to [contact]

Deviations and violations are non-compliance events discovered after the event has occurred. Deviation logs will be maintained for each site in multi-centre studies. An alternative frequency of deviation log submission to the sponsors may be agreed in writing with the sponsors.

12.3 SERIOUS BREACH REQUIREMENTS

A serious breach is a breach which is likely to effect to a significant degree:

- (a) the safety or physical or mental integrity of the participants of the trial; or
- (b) the scientific value of the trial.

If a potential serious breach is identified by the Chief investigator, Principal Investigator or delegates, the co-sponsors ([contact]) must be notified within 24 hours. It is the responsibility of the co-sponsors to assess the impact of the breach on the scientific value of the trial, to determine whether the incident constitutes a serious breach and report to research ethics committees as necessary.

12.4 STUDY RECORD RETENTION

All study documentation will be kept for a minimum of 3 years from the protocol defined end of study point. When the minimum retention period has elapsed, study documentation will not be destroyed without permission from the sponsor.

12.5 END OF STUDY

The end of study is defined as the last participant's last visit.

The Investigators or the co-sponsor(s) have the right at any time to terminate the study for clinical or administrative reasons.

The end of the study will be reported to the REC, and R+D Office(s) and co-sponsors within 90 days, or 15 days if the study is terminated prematurely. The Investigators will inform participants of the premature study closure and ensure that the appropriate follow up is arranged for all participants involved. End of study notification will be reported to the co-sponsors via email to [contact].

A summary report of the study will be provided to the REC within 1 year of the end of the study.

12.6 CONTINUATION OF TREATMENT FOLLOWING THE END OF STUDY

All participants will continue on treatment following the end of study in line with usual clinical practice.

12.7 INSURANCE AND INDEMNITY

The co-sponsors are responsible for ensuring proper provision has been made for insurance or indemnity to cover their liability and the liability of the Chief Investigator and staff.

The following arrangements are in place to fulfil the co-sponsors' responsibilities:

- The Protocol has been designed by the Chief Investigator and researchers employed by the University and collaborators. The University has insurance in place (which includes no-fault compensation) for negligent harm caused by poor protocol design by the Chief Investigator and researchers employed by the University.
- Sites participating in the study will be liable for clinical negligence and other negligent harm to individuals taking part in the study and covered by the duty of care owed to them by the sites concerned. The co-sponsors require individual sites participating in the study to arrange for their own insurance or indemnity in respect of these liabilities.
- Sites which are part of the United Kingdom's National Health Service will have the benefit of NHS Indemnity.
- Sites outwith the United Kingdom will be responsible for arranging their own indemnity or insurance for their participation in the study, as well as for compliance with local law applicable to their participation in the study.

